For participants who have a case of ARVI (COVID-19), visit 3 can be carried out earlier or later, but the total duration of the study should not be more than 90 days. Up to this point, medical researcher should try to collect the most complete information about the patient's condition. If it is not possible to conduct a face-to-face visit, final visit is conducted remotely.

Schedule of research procedures

| Visit number | 0 | 1 | 2 | 3 |
|---|-----------|---------------|--|--|
| Setting | In person | In person | Phone call | In person |
| Visit name | Screening | Randomization | The end of the course of prevention Beginning of the observation period | End of the observation period Completion of the study |
| Study days | -3-1(0) | 0 | 27 (+/-3) | 56-62* |
| Informed consent ¹ | + | | | |
| Anamnesis ² | + | | | |
| Complaints | + | + | + | + |
| Physical examination ³ | + | + | | + |
| Pregnancy test | + | | | |
| Safety assessment | + | + | + | + |
| Analysis for RNA to SARS-CoV-2 ⁴ | + | | | + |
| Checking the inclusion/non-inclusion criteria | + | + | | |
| Checking exclusion criteria | | | + | |

⁷ A full-time visit can be carried out both at the research center and at home

| | | | | |
|--|---|---|---|----------------|
| Randomization | | + | | |
| Delivery of the study drug ⁵ | | + | | + |
| Compliance assessment | | | + | + |
| Issue of the participant's diary | | + | | |
| Effectiveness evaluation | | | + | + |
| Assessment of the participant's condition according to the WHO scale | + | + | + | + ⁷ |
| Return of study drug and diary | | | | + |

* For patients with a registered case of ARVI, duration of participation in the study may be longer, but not exceed 90 days

- 1 All research procedures, except routine laboratory and instrumental studies, the data of which are used to assess the condition of the study participant, are performed after the procedure of signing the informed consent of the patient
- 2 The study should indicate the epidemiological history of respiratory viral diseases, status of vaccination (influenza, pneumonia, COVID-19), use of means of nonspecific protection and prevention of acute respiratory viral infections, including COVID-19

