In this study, the main parameter of effectiveness is the proportion of patients with acute respiratory viral infections, including COVID-19, at the end of the period of preventive administration of the drug. The study is planned to show that in the study group, the number of patients with acute respiratory viral infections, including COVID-19, will be significantly less compared to the control group.

The efficiency parameter was selected based on international recommendations for manufacturers of medicines and biological products [28].

The null hypothesis will be tested by comparing the number of cases in the two groups at the end of the period of preventive administration of the drug. It is expected that at least 90% of randomized patients will be suitable for inclusion in the population of the primary analysis (PP). The statistical purpose of the study is a comparative study of the effectiveness of the preventive regimen of the drug. In the main group of study I, study drug Ingaron 100,000 IU, lyophilizate, will be used to prepare a solution for intranasal administration, 1 time a day every other day for 10 days with a repeat of the 10-day course of preventive administration after 7 days of interruption.

To estimate the sample size in this study, an 80% power level was taken (P – probability of not missing the present effect is 0.8) and a one-sided level of statistical significance of 5% (α – the probability of making an erroneous decision about the presence of an effect is less than 0.05). The statistical criteria used are one-sided due to the availability of information about the superiority of the effect of the study drug over the lack of preventive measures against the nosology being studied [28].

Thus, the sample size was calculated based on the following parameters:

- at the required significance level $\alpha = 0.05$, the value of $Z = 1.96$;
- level of statistical power is assumed to be 80%, the value of $Z = 0.84$;
- method of sample formation – randomization using random elements.

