The primary criterion of effectiveness is the proportion of patients with acute respiratory viral infections, including COVID-19, at the end of the period of preventive administration of the drug (measurement time: 28 days). Secondary efficacy criteria: proportion of patients with confirmed COVID-19 at the end of the period of preventive administration of the drug (measurement period: 28 days); proportion of patients with acute respiratory viral infections, including COVID-19, at the end of the follow-up period (change period: 2 months); proportion of patients with confirmed COVID-19 at the end of the follow-up period (period of change: 2 months); and the frequency of development of complicated course of ARVI.

The literature analysis conducted on similar studies of the effectiveness and safety of the use of interferon-gamma shows that the incidence of ARVI can be observed in 2% of cases in the main group of patients taking interferon gamma, as well as in 14% of the control group taking alternative methods of protection and representing medical workers working in the "red zone" and those at high risk through frequent and prolonged contact with infected patients ($p < 0.05$).

Provided incidence in the control group is from 1 to 5% (taking into account the assumption that the incidence in the control group will be approximately equal to the average incidence of the general population) [29], and incidence in the study group will be at least 3% lower (which can already be considered a minimally clinically significant decrease in incidence in the absence of preventive measures with proven effectiveness, which could be taken as a standard), minimum sample size should be 630 patients (taking into account 10% of early retirement). Such a sample size will also make it possible to establish a decrease in incidence by 4% or more when incidence is set at up to 8% in the control group and a decrease in incidence by 6% or more when the incidence is set at up to 18% in the control group (Table 1 – Dependence of the sample size on various parameters).

The calculation of the required sample size was performed using a formula for calculating the sample size for a qualitative sign [30]:

$$n = \frac{P_1 * Q_1 * t^2 + P_2 * Q_2 * t^2}{(P_1 - P_2)^2}$$

Note to the formula:

P – proportion of cases in which the study sign occurs,

Q – proportion of cases in which the study sign does not occur,

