Analysis of the source data

Demographic characteristics, baseline, and follow-up characteristics such as anamnesis, comorbidities and medications used will be described by treatment groups for the ITT population and then safety, if they differ.

⁶ URL <https://www.R-project.org/>

⁷ <https://www.r-project.org/doc/R-FDA.pdf>

Primary Endpoint Analysis

The main parameter of the effectiveness of the preventive use of Ingaron® is the proportion of patients with acute respiratory viral infections, including COVID-19, at the end of the period of preventive administration of the drug (measurement time: 28 days).

In accordance with the purpose and objectives of the study, the null and alternative hypotheses are formulated as follows:

- Null hypothesis (H_0) consists in the assumption that the prophylactic administration of Ingaron will not lead to a change in the incidence of acute respiratory viral infections, including COVID-19, among adult volunteers;
- Alternative hypothesis (H_a) is that in the study group, the proportion of ARVI cases, including COVID-19, will differ from the control group.

$$H_0: \mu_1 = \mu_2$$

$$H_a: \mu_1 \neq \mu_2,$$

where μ is the fraction of the main variable for the corresponding group.

To test these hypotheses, the method of a two-way variant of the Fisher's exact test (with expected frequencies less than 5) or the Pearson's chi-squared test (χ^2) (with the Yates correction for expected frequencies more than 5, but less than 10) will be used.

In all cases, the significance level (α is the probability of an error of the first kind) 0.05 will be used.

The analysis of the primary efficiency parameter will be carried out on the ITT population (main analysis), as well as – additionally – on the PP population (additional analysis).

Data on the case of ARVI (COVID-19) is collected during the entire study by filling out a form on the registration of a case of ARVI.

Secondary Endpoint analysis

The following secondary efficacy parameters in this study are quantitative indicators that will be compared between treatment groups:

- proportion of patients with confirmed COVID-19 at the end of the period of preventive administration of the drug (measurement period: 28 days);
- proportion of patients with acute respiratory viral infections, including COVID-19, at the end of the observation period (change period: 2 months);
- percentage of patients with confirmed COVID-19 at the end of the follow-up period (change period: 2 months);

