5.2. The size of the sample under study

The estimation of the sample size of subjects was based on the following parameters:

- bilateral significance level $\alpha=0.05$ Z value = 1.96;
- statistical power level is 80%, Z-value = 0.84;
- method of sample formation — randomization using elements of randomness;
- statistical criteria used are two-sided due to the lack of a posteriori information about the superiority of the effect of the study drug over the placebo effect.

Calculation results:

- number of volunteers who must complete participation in the study in accordance with the protocol is 286 in the group or a total of 572 participants.
- number of randomized participants is 315 in a group or total 630 people
- number of screened volunteers – up to 642.

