6. TABLE PATTERNS

Table1. Distribution of subjects

Distribution of subjects	Group I (proportion, %)	Group II (proportion, %)
Included in the study (screened)	n/N (%)	
Of these:		
Excluded at the screening stage:	n/N (%)	
Randomized	n/N (%)	n/N (%)
Prematurely excluded, out of them:	n/N (%)	n/N (%)
Existence of exclusion criterion #X (description)	n/N (%)	n/N (%)
Population safety	n/N (%)	n/N (%)
ITT population	n/N (%)	n/N (%)
Population PP	n/N (%)	n/N (%)

Table2. Demographic and anthropometric characteristics of subjects at the time of inclusion (safety population)

Group	Parameter	Age (years)	Weight (kg)	Height (cm)	Smoking index (p/y)	Frequency of acute respiratory infections (amount/g)
GROUP I	n					
	M					
	CO					
	min.					
	max.					
	Me					
GROUP II	n					
	M					
	CO					
	min.					
	max.					
	Me					
p (between groups)						

Table3. Distribution of subjects by gender (safety population)

Gender	GROUP I	GROUP II
Male	n/N (%)	n/N (%)
Female	n/N (%)	n/N (%)
p (between groups)		

Table4. Distribution of subjects by race (safety population)

Race	GROUP I	GROUP II
Caucasian	n/N (%)	n/N (%)
Mongoloid	n/N (%)	n/N (%)
Negroid	n/N (%)	n/N (%)
p (between groups)		

Table5. Medical history (safety population)

Parameter	Value	Group I (N =)	Group II (N =)
Diagnosis (chronic disease)	...	n/N (%)	n/N (%)
Diagnosis (according to anamnesis)	...	n/N (%)	n/N (%)
p (between groups)			

Table 6. Methods of nonspecific prevention (safety population)

Type	Frequency	GROUP I	GROUP II
Total subjects		N =	N =
Masks	Yes	n/N (%)	n/N (%)
	No	n/N (%)	n/N (%)
	Sometimes	n/N (%)	n/N (%)
Respirator	Yes	n/N (%)	n/N (%)
	No	n/N (%)	n/N (%)
	Sometimes	n/N (%)	n/N (%)
Gloves	Yes	n/N (%)	n/N (%)
	No	n/N (%)	n/N (%)
	Sometimes	n/N (%)	n/N (%)
Glasses	Yes	n/N (%)	n/N (%)
	No	n/N (%)	n/N (%)
	Sometimes	n/N (%)	n/N (%)
Surgical overalls	Yes	n/N (%)	n/N (%)
	No	n/N (%)	n/N (%)
	Sometimes	n/N (%)	n/N (%)
p (between groups)			

Table 7. Drug allergy (safety population)

	GROUP I	GROUP II
Total subjects	N =	N =
No	n/N (%)	n/N (%)
Yes	n/N (%)	n/N (%)
p (between groups)		

Table 8. Results of the assessment of the incidence rate at the end of the prevention period (ITT/PP/ITT_NV/PP_NV/ITT_NV_BE/PP_NV_BE population)

	GROUP I	GROUP II
Total subjects	N =	N =
ARVI	n/N (%)	n/N (%)
Not sick	n/N (%)	n/N (%)
p (between groups)		

Table 9. Results of the assessment of the incidence of COVID-19 at the end of the prevention period (ITT population, PP)

	GROUP I	GROUP II
Total subjects	N =	N =

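### The primary ARVI comparison is a valid but unadjusted 2x2 whose effect size gets a confidence interval only if significant; a prespecified baseline-adjusted risk difference would be a small, cheap gain

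*SAP*

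**What the plan says.** SAP 5.1 (Primary Endpoint Analysis) names the main parameter, read at day 28, as "the proportion of patients with acute respiratory viral infections, including COVID-19, at the end of the period of preventive administration of the drug (measurement time:" …). The test is: "To test these hypotheses, the method of a two-way variant of the Fisher's exact test (with expected frequencies less than 5"), or Pearson's chi-squared with a Yates correction for expected counts between 5 and 10. It is run in ITT as the main analysis and repeated in PP. Neither document plans a regression or a stratified analysis of this endpoint. SAP 2.2 describes balanced-block randomisation and names no stratification factor.

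Baseline risk information is available. Note 2 to the Protocol's Schedule of research procedures says of the screening history: "The study should indicate the epidemiological history of respiratory viral diseases, status of vaccination (influenza, pneumonia, COVID-19"), and it adds nonspecific protection. SAP Table 2, which describes participants at inclusion, has a column "Frequency of acute respiratory infections (amount/g"). Tables 2 to 7 and Table 24 end in between-group p-values.

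Vaccination has one further role. SAP 5.4 and 5.5 define four additional populations by COVID-19 vaccination status (ITT_NV, PP_NV, ITT_NV_BE, PP_NV_BE). Table 8 repeats the primary comparison in each of them.

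On estimation, SAP 5.1 makes a confidence interval for the size of the group difference conditional on a significant result. Table 8 holds counts, percentages and a p-value, with no effect estimate.

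**The concern.** Prior infection frequency and vaccination plausibly predict who falls ill within 28 days. With few events, a chance imbalance in either moves the crude estimate, and the plan has no prespecified analysis that would allow for it. The study is open-label, so an adjustment chosen after the data are seen would be open to challenge.

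The conditional interval matters more for the reader of the results. If the test is not significant, which is close to an even chance at the planning case, the plan yields a p-value and two percentages. It then gives no statement of which effects remain compatible with the data.

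**Working it through.** **Inputs.** The Protocol (Number of participants) says "incidence in the control group is from 1 to 5" per cent and a reduction of at least 3 points, so the planning row is 5% v 2%. It gives 286 completers and 315 randomised per arm. SAP 5.2 says "statistical power level is 80%, Z-value = 0.84" and "statistical criteria used are two-sided due to the lack of a posteriori information". The Protocol instead states "a one-sided level of statistical significance of 5" per cent while using Z = 1.96. The two documents must be reconciled; the SAP's two-sided 0.05 is used here. Neither document gives the strength or prevalence of any risk factor, so those below are assumptions.

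**1. The plan's own figure.** The printed formula n = t²(P1Q1 + P2Q2)/(P1 − P2)² gives 1.96² × (0.0475 + 0.0196)/0.03² = 286.4, and 286 × 1.1 = 314.6, i.e. 315. The figures reproduce, but the formula has no power term.

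**2. The planned test.** Expected events at 315 per arm are 15.75 + 6.3 = 22.05. By exact enumeration of the SAP's rule at 315 per arm, type I error at 5% v 5% is 5.1% (4.9% at 286) and power at 5% v 2% is 51.7% (45.9% at 286). The test holds its level.

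**3. Unadjusted precision.** The variance of the risk difference is 0.0671/315 = 0.00021302, so the standard error is 1.46 points. Approximate power is Φ(0.03/0.014595 − 1.96) = 53.8%.

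**4. One binary risk factor.** With prevalence q and the same treatment risk ratio in both strata, the adjusted variance is Σw[p_c(1 − p_c) + p_t(1 − p_t)]/n + Σw(d − d̄)²/(2n), where w is the stratum share and d the stratum risk difference. Take a risk ratio of 14/3 = 4.67 (the Protocol's 14% in red-zone staff over the middle of 1 to 5%) and q = 0.3:
- Control risks are 2.38% and 11.11%; treated risks are 0.95% and 4.44%.
- Within-stratum part: (0.7 × 0.032676 + 0.3 × 0.141235)/315 = 0.00020712.
- Between-stratum part: 0.000576/630 = 0.00000091.
- Total 0.00020804, a fall of 2.3%; power 54.8%.

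Across risk ratios of 2 to 4.67 and prevalences of 10 to 50%, variance falls by 0.3 to 2.4% (power 53.9 to 54.8%). At a risk ratio of 14 it falls by 2.7 to 10.5% (power 54.9 to 58.4%).

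**5. A continuous risk score.** For an AUC of about 0.63, 0.71, 0.79 and 0.85, variance falls by 0.9, 2.6, 6.5 and 12.1%. Power is 54.2, 54.9, 56.6 and 59.2%.

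**6. Chance imbalance.** One standard deviation of imbalance is √(2q(1 − q)/315), or 3.65 points at q = 0.3. With a risk ratio of 4.67 the stratum gap averages (8.73 + 3.49)/2 = 6.11 points over the arms, so the risk difference shifts by 0.0365 × 6.11 = 0.22 points. Over risk ratios of 2 to 4.67 the shift is 0.08 to 0.22 points, and up to 0.47 at 14. The standard error is 1.46.

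**7. Simulated models, 5% v 2%, 315 per arm.** Variance is relative to the crude difference; covariate effects are assumed.
- Unpenalised logistic, standardised: 0.98 to 1.00 in one set of runs and 0.95 to 1.00 in another. Type I error was about 4.5 to 6%.
- Firth-penalised: 0.98 to 1.05, with arm risks inflated (2.0% to about 2.2%, 5.0% to about 5.3%).
- Ridge: shrinking the arm term biased the effect toward zero and cost 6 to 8 power points. A separate ridge run under the strongest covariate assumptions reached 0.93, with power rising from 0.517 to 0.562. The result therefore depends on how the penalty is set.

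**8. Against the size of the trial.** Reaching 80% power at 315 per arm needs a variance of (0.03/2.8016)² = 0.00011467, a cut of 46%. By sample size it needs 588 per arm two-sided, or 463 one-sided.

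**The case against.** The strongest reply is that nothing is wrong. Randomisation makes the crude test valid, the gain at the planning case is within simulation noise, and a regression on about 22 events brings fragility that a 2x2 does not have. Most of this stands. It is why the 2x2 should remain the primary test and the model should have no more than two covariates. It does not answer the conditional interval, which withholds the effect estimate's precision when that is most needed.

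Several stronger readings are tempting, and the documents do not support them:
- A reader might infer that the baseline data serve only to print p-values. Vaccination status does define sensitivity populations for the primary endpoint (SAP 5.4, 5.5, Table 8). That is restriction rather than adjustment, but the variable is used.
- A reader might infer that adjustment is needed to keep vaccinated participants. The main ITT analysis removes nobody for vaccination; only the additional sets do. The SAP 5.4 exclusion concerns vaccination during the study, which a pre-randomisation covariate does not address.
- A reader might expect a sizeable gain from vaccination. Some simulations assumed 20% vaccinated before entry with relative risk 0.4 for all ARVI, whereas a footnote to SAP 5.4 calls the vaccinated proportion small.
- Protective equipment looks like a natural covariate. The Protocol records it at screening and has preventive measures entered in the diary after open allocation. Table 6 does not say which is shown.

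**Conclusion.** The point holds as a minor refinement. The primary test is sound. Two predictors available at entry are not adjusted for, and the risk difference has an interval only after a significant result.

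Under assumed but plausible risk-factor strengths, adjustment is worth about 0 to 5% in variance and 0 to 3 power points at 5% v 2%. Larger gains (10 to 12% in variance, about 5 points) need a risk ratio near 14 or an AUC near 0.85. None of this approaches the 46% cut that 80% power would require, so it does not repair the sample-size shortfall. The surer benefit is a risk difference with an interval in every outcome of the trial.

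One practical limit follows from sparse data. If only 5% were vaccinated before entry with relative risk 0.4 (both assumptions), average risk 3.5% implies 0.4 × 0.035/(0.95 + 0.05 × 0.4) = 1.44% among 31.5 people, or 0.45 expected events. The chance of none is about e^−0.45 = 0.64. The fallback below may well be used.

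**What to change.** - Keep the Fisher/chi-squared test as the primary test and the source of the primary p-value.
- Prespecify, in all ITT participants and regardless of significance, a marginal risk difference with robust 95% CI. Standardise it from an unpenalised logistic model with arm, annual respiratory-infection frequency and COVID-19 vaccination before randomisation (yes/no). Use no Firth penalty and no ridge on the arm term.
- Take vaccination from the screening history, because Table 24 does not separate vaccination before entry from vaccination during the study.
- State a rule that keeps participants with a missing covariate, for example a missing-indicator category. SAP 5.3 analyses available data only, so without a rule a regression would drop them.
- If the model does not converge, report the unadjusted risk difference with its CI. Say that a vaccination group with no events counts as non-convergence.
- Add the estimate and interval to Table 8, and remove the condition on significance in SAP 5.1.
- Optionally drop the p-values from Tables 2 to 7. Randomisation already makes their null hypothesis true, and removing them changes no result.

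The cost is SAP wording and a few lines of code, with no new data. The downside is some extra analysis work and one model on about 22 events, which limits it to two covariates.

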- ❖ All participants included in the study (FAS, Full Analysis Set). This population will be used to describe basic characteristics, including demographic and anthropometric indicators, data on concomitant diseases, and will also be used as the main population to assess performance parameters. In this case, the participant's group will be determined by the "intention to treat" (ITT Analysis).
- ❖ Auxiliary analysis of effectiveness parameters is planned for all subjects who completed the study without significant deviations from the study protocol (PP, Per Protocol).

Methods of descriptive statistics

For numerical indicators, such as demographic and anthropometric data (body weight, age, height, BMI), as well as numerical performance parameters will be calculated:

- Number of missing values (N);
- Minimum value (Min);
- Maximum value (Max);
- Arithmetic Mean (M);
- Standard Deviation (SD);
- 95 % confidence interval (CI) for the mean;

- Median (Me).

For qualitative variables (frequency of AE/SAE development, for example), absolute number in the n/N format will be given, as well as the percentage (%).

Analysis of basic characteristics

The distribution of subjects, demographic and baseline characteristics will be presented using descriptive statistics methods for all subjects included in the study (FAS-population). An intergroup comparison of the basic quantitative characteristics will be carried out using the t-test (or the Mann-Whitney test), depending on the type of data distribution. For categorical data, the χ^2 -criterion or Fisher's exact test will be applied if the expected frequency in any of the cells is less than 5.

Standard methods available in the XLSTAT 2020.3 program will be used for data analysis.

When analyzing numerical data, preliminary testing of variables for the normality of the distribution will be carried out using Shapiro-Wilk's test, as well as a test for asymmetry and kurtosis with an indication of the p value when testing the null hypothesis of the normal distribution of the variable. In the case of a normal distribution, an intra-group comparison of parameter changes is carried out using a paired t-test. For a comparative evaluation, the χ^2 -criterion or the exact Fisher test will be used if the expected frequency in any of the cells is less than 5.

Significance level

A significance level of 0.05 will be used in all tests. Correction for the multiplicity of comparison is not introduced.

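### The SAP's Yates band for the primary test conflicts with the SAP's own general rule, switches where the 5% v 2% scenario expects its data, and costs power when incidence is below about 4%

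*SAP*

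**What the plan says.** SAP section 5.1, Primary Endpoint Analysis, sets a three-way rule: two-sided Fisher when expected frequencies are below 5; Pearson chi-squared "with the Yates correction for expected frequencies more than 5, but less than 10"; and, by implication, uncorrected Pearson from there on. Values of exactly 5 and exactly 10 are not assigned. The level is fixed: "In all cases, the significance level (α is the probability of an error of the first kind) 0.05 will be used". The Secondary Endpoint paragraph repeats the rule for the binary secondary endpoints.

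Earlier in section 5.1 the SAP gives a general rule for categorical data with two branches only, chi-squared, or Fisher when any expected count is below 5. The protocol (Statistical Methods, Analysis of basic characteristics) has the same two branches: the "exact Fisher test will be used if the expected frequency in any of the cells is less than 5". The protocol does not tie that sentence to the primary endpoint.

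SAP section 5.1 promises confidence intervals for group differences only where a significant difference is found.

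For planning, the protocol (Number of participants) writes "Provided incidence in the control group is from 1 to 5" per cent and "incidence in the study group will be at least 3% lower". It adds a 4-point drop from up to 8% and a 6-point drop from up to 18%. It plans 286 completers and 315 randomised per group.

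**The concern.** Two rules in one SAP section can give different p-values for the same primary table. The extra band is also placed where the scenario behind the sample size expects its data. The Yates correction and Fisher's test keep the true error rate well under the nominal level when events are few, so the test may miss a real effect that a standard alternative would detect. A switch that depends on the total number of cases can also rank results in the wrong order. At stake are the verdict on the primary endpoint in borderline tables and some power in a trial that has little to spare.

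**Working it through.** **Inputs.** Two-sided 0.05 (SAP 5.1; SAP 5.2 says "statistical criteria used are two-sided due to the lack of a posteriori information"). The protocol's sample-size text instead has "a one-sided level of statistical significance of 5" per cent, yet uses Z = 1.96; I follow the SAP. Arms of 286 and 315. Scenarios 5 v 2, 4 v 1, 3 v 0, 8 v 4 and 18 v 12%.

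**The plan's own figure.** The protocol formula n = (P1Q1 + P2Q2)t²/(P1 − P2)² with t = 1.96 gives (0.0475 + 0.0196) × 3.8416 / 0.0009 = 286.4, and 286.4 × 1.1 = 315.05. The sample size therefore reproduces. SAP 5.2 states "statistical power level is 80%, Z-value = 0.84", but 0.84 does not enter the formula. The usual two-proportion formula needs about 588 per arm for 80% power, two-sided, at 5 v 2%.

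**Where the switch falls.** With equal arms the smallest expected count is half the total number of cases. At 5 v 2% and 286 per arm the expected total is 286 × 0.07 = 20.0, so the expected count is 10. With 315 it is 315 × 0.07 / 2 = 11.0.

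**Two neighbouring tables, 286 per arm.** With N = 572, m cases in total and difference d, Pearson is N·d²/[m(N − m)]; Yates replaces d by d − 1.
- 14 v 5 (m = 19, expected 9.5, Yates applies): 572 × 64 / (19 × 553) = 3.48, p = 0.062. Uncorrected: 572 × 81 / 10507 = 4.41, p = 0.036.
- 15 v 6 (m = 21, expected 10.5, Pearson applies): 572 × 81 / (21 × 551) = 4.00, p = 0.045.

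The case difference is the same and the relative effect is weaker (6/15 = 0.40 against 5/14 = 0.36), yet only the second table is significant.

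**True size of the SAP rule** (all 2×2 tables enumerated from two binomials, 286 per arm): 1.1% at 1% common incidence, 2.3% at 2%, 3.2% at 3%, 4.4% at 4%, 4.9% at 5%, and 5.1% at 6 to 8%. Its maximum is about 5.1% at 286 per arm and 5.2% at 315, the same as for uncorrected Pearson.

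**Power (%) by the same enumeration.** Losses quoted afterwards are taken before rounding.

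| Per arm | Scenario | SAP rule | Yates band removed | Pearson | Mid-p |
|---|---|---|---|---|---|
| 286 | 5 v 2 | 45.9 | 50.7 | 50.7 | 50.1 |
| 286 | 4 v 1 | 55.6 | 65.8 | 66.8 | 64.2 |
| 286 | 3 v 0 | 86.0 | 86.0 | 97.3 | 93.2 |
| 286 | 8 v 4 | 53.1 | 53.1 | 53.1 | 51.5 |
| 286 | 18 v 12 | 52.4 | 52.4 | 52.4 | 51.9 |
| 315 | 5 v 2 | 51.7 | 54.7 | 54.7 | 54.4 |
| 315 | 4 v 1 | 61.6 | 70.9 | 71.3 | 69.2 |
| 315 | 3 v 0 | 91.2 | 91.2 | 98.6 | 96.1 |
| 315 | 8 v 4 | 57.5 | 57.5 | 57.5 | 55.7 |
| 315 | 18 v 12 | 56.4 | 56.4 | 56.4 | 55.8 |

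N-1 chi-squared matches Pearson in the first three scenarios. In the two higher ones it is between 0 and 0.8 points lower. Against Pearson the SAP rule loses 4.9 (5 v 2) and 11.3 points (4 v 1) at 286, and 3.1 and 9.8 at 315. Against mid-p it loses 4.2 and 8.6 at 286, and 2.7 and 7.6 at 315. At 3 v 0 the loss comes from the Fisher branch, so removing the Yates band alone recovers none of it.

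**How often the rules disagree.** The primary-endpoint rule and the SAP's own general rule reach opposite verdicts in 4.9% of trials at 5 v 2 and 10.3% at 4 v 1 with 286 per arm (3.1% and 9.3% with 315).

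**The case against.** The rule is prespecified and conventional, and it depends only on the pooled number of cases. Conservatism protects against a false claim. Boschloo's test, which strictly holds 5%, gains only 0.3, 3.1 and 0.0 points over the SAP rule at 5 v 2, 4 v 1 and 3 v 0% with 286 per arm, and is 4.0 and 1.5 points worse at 8 v 4 and 18 v 12%. The main analysis is ITT, so 315 per arm may be nearer than 286. The protocol's test sentence stands under baseline characteristics.

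Much of this stands as a limit on scope. A reader might infer that the rule costs power throughout the trial. The documents do not support that: in their own 8 v 4% and 18 v 12% scenarios the rule is almost always plain Pearson and nothing is lost. A reader might also infer the same loss on every binary secondary endpoint. No rates are assumed for those, and the two-month ARVI endpoint accumulates more cases, which moves it towards the Pearson branch. Nor does the protocol directly contradict the SAP on the primary test, since it names no test specifically for that endpoint. The firmer conflict is inside SAP 5.1.

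The defence of conservatism does not carry as far. The SAP rule does not hold 5% strictly either. Its worst-case size equals that of uncorrected Pearson, so the Yates band lowers the error rate only where events are few and buys nothing in the worst case.

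**Conclusion.** The point holds, limited to low incidence. SAP 5.1 gives two different rules for the primary table. The one written for the primary endpoint has a switch that falls at the expected data of the 5 v 2% scenario and can call a weaker result significant and a stronger one not. When pooled incidence is below about 4%, it costs about 3 to 11 points of power against chi-squared, or 3 to 9 against mid-p, across 5 v 2 and 4 v 1% and the two arm sizes.

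This is the smaller power problem. Power at 5 v 2% is only 46 to 55% under any rule in the table, against the stated 80%, because the sample-size formula has no power term. A reader might infer that a better test restores the planned power; it does not.

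Assumptions: two-sided 0.05; equal arms; expected frequency read as the smallest expected cell; exactly 5 or 10 assigned to the upper band (sending 10 to Yates leaves power unchanged at these sizes).

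**What to change.** Name one test for the primary endpoint, whatever the cell counts, and state it identically in the SAP 5.1 general rule, SAP 5.1 Primary Endpoint Analysis and the protocol's Statistical Methods. Use the same test in the Secondary Endpoint paragraph. Remove the Yates step. Either choice is defensible:
- **Uncorrected or N-1 chi-squared.** This recovers the full low-incidence loss. True size can exceed 5% by about 0.1 to 0.2 point, as the SAP rule's already does.
- **Two-sided Fisher mid-p.** True size stays at or below 4.9% for incidence from 0.5 to 8%, but it costs about 0.5 to 1.8 points of power in the 8 v 4% and 18 v 12% scenarios.

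Report a matching 95% confidence interval for the risk difference whatever the p-value. The cost is wording in two documents and a short analysis program in R, with no new data. If only the Yates band is dropped and Fisher kept below 5, nearly all the loss at 5 v 2% and 4 v 1% is recovered and none at 3 v 0%. Recompute the sample size for the chosen test as a separate step.
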